11.1 Appendix A: Exclusion Criteria for the Per Protocol Populations

The following criteria will be used to further exclude subjects from the PP population:

- Subject received incomplete dose of study drug.
- Subject received prohibited medication that could potentially confound the efficacy outcome.

11.2 Appendix B.1.1: Urticaria Patient Daily Diary for Patient with Cholinergic Urticaria

- 1) Did you do anything today that normally triggers symptoms?
 - No
 - Yes, with low intensity
 - Yes, with moderate intensity

- Yes, with high intensity
 - What exactly?

2) Did you have hives today?

- No
- Yes, with low intensity
- Yes, with moderate intensity
- Yes, with high intensity

3) Did you have any itching today?

- No
- Yes, with low intensity
- Yes, with moderate intensity
- Yes, with high intensity

4) How would you rate your symptoms overall today?

- Mild, easy to tolerate
- Moderate, quite noticeable, certain limitations
- Very intense, very noticeable, considerable limitations

5) Have you taken your daily tablet of antihistamines in the last 24 hours?

- No _____ Yes _____

6) Have you taken any rescue medication in the last 24 hours?

- No _____ Yes _____

How many

- 1 tablet, 2 tablet, 3 tablet

7) Have you taken any other medications besides your regular medications in the last 24 hours (for example, pain tablets, cortisone, ...)?

- No _____ Yes _____

How many

- 1, 2, ..., 10

Medication

- Drug taken: Today _____ Yesterday _____ Another Date _____
- Medication name _____ Indication _____ Dosage (mg) _____

How often during the study _____

11.3 Appendix B.1.2: Urticaria Patient Daily Diary for Patient with Urticaria Factitia

1) Were you free of your urticaria factitia symptoms today?

- No _____ Yes _____

2) Please rate your urticaria factitia symptoms in the last 24 hours.

- VAS (0 means no symptoms; 10 means maximum symptoms)

3) Please rate your symptoms of redness and hives in the last 24 hours.

- Redness VAS (0 means no symptoms; 10 means maximum symptoms.)
- Hives VAS (0 means no symptoms; 10 means maximum symptoms.)

4) How severe was the average and maximum itching caused by the urticaria factitia in the last 24 hours?

- Average itching VAS (0 means no symptoms; 10 means maximum symptoms.)
- Maximum itching VAS (0 means no symptoms; 10 means maximum symptoms.)

5) For how many hours did you have itching caused by urticaria factitia in the last 24 hours?

- <3 hours _____ 3–12 hours _____ >12 hours _____

6) How much did the disease impair your quality of life in the last 24 hours?

- Not at all _____ Somewhat _____ Much _____ Very much _____

7) How often did you avoid stimuli in the last 24 hours that are known to result in symptoms?

- Not at all _____ Somewhat _____ To a great extent _____ Completely _____

8) Have you taken your daily tablet of antihistamines in the last 24 hours?

- No _____ Yes _____

9) Have you taken rescue medication in the last 24 hours?

- No _____ Yes _____

How many

- 1 tablet _____ 2 tablet _____ 3 tablet _____

10) Have you taken any other medications besides your regular medications in the last 24 hours (for example, pain tablets, cortisone,)

- No _____ Yes _____

How many

- 1 __, 2 __,, 10 __
- Drug taken: Today _____, Yesterday _____, Another Date _____
- Medication name _____, Indication _____, Dosage (mg) _____,

How often during the study _____

11) Please indicate if provocation test was performed

- Yes _____ No _____

Indicate if hives and/or redness occurred 10 minutes after provocation, and how severe your itching was.

- Hives: Yes _____ No _____
- Redness: Yes _____ No _____
- Itching: NRS: 0 (no itching), 1, 2, ..., 10 (max itching imaginable)

11.4 Appendix B.1.3 Urticaria Patient Daily Diary for Patients with Chronic Spontaneous Urticaria

Diary of Symptoms

1) Symptoms and medication use in the last 24 hours

- Hives: None _____ <20 _____ 20–50 _____ >50 _____
- Itching: None _____ Mild _____ Moderate _____ Severe _____

2) Did you use the daily antihistamine tablet in the last 24 hours?

- No _____ Yes _____

3) Did you use any rescue medication in the last 24 hours

- No _____ Yes _____

How many

- 1 tablet _____ 2 tablets _____ 3 tablets _____

4) Did you use any other medications in the last 24 hours

- No _____ Yes _____

How many

- 1 __, 2 __, ..., 10

- Drug taken: Today _____, Yesterday _____, Another Date _____

- Medication name _____, Indication _____, Dosage (mg) _____

How often during the study _____

11.5 Appendix B.2: Urticaria Control Test

The Urticaria Control Test (UCT) is a simple 4-item tool. A score between 0 and 4 is assigned to every answer option. Subsequently, the scores for all 4 questions are summed up. Accordingly, the minimum and maximum UCT scores are 0 and 16, with 16 points indicating complete disease control. UCT questions and the score for each answer option are as follows.

1) How much have you suffered from the physical symptoms of the urticaria (itch, hives (welts) and/or swelling) in the last four weeks?

O very much (0 points)	O much (1 point)	O somewhat (2 points)	O a little (3 points)	O not at all (4 points)
---------------------------	---------------------	--------------------------	--------------------------	----------------------------

2) How much was your quality of life affected by the urticaria in the last 4 weeks?

O very much (0 points)	O much (1 point)	O somewhat (2 points)	O a little (3 points)	O not at all (4 points)
---------------------------	---------------------	--------------------------	--------------------------	----------------------------

3) How often was the treatment for your urticaria in the last 4 weeks not enough to control your urticaria symptoms?

very much much somewhat a little not at all
(0 points) (1 point) (2 points) (3 points) (4 points)

[figure not shown]
4) Overall, how well have you had your urticaria under control in the last 4 weeks?

[figure not shown]
very much much somewhat a little not at all
(0 points) (1 point) (2 points) (3 points) (4 points)

[figure not shown]
Cut off-value of ≤ 11 is usually recommended (<12: poorly controlled urticaria, ≥ 12 : well controlled urticaria).

[figure not shown]
[figure not shown]
Reference: www.moxie-gmbh.de

[figure not shown]

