#### 10.4.2 Urticaria Control Test

The urticarial control test (UCT) is an instrument that is valid in all types of chronic urticaria, not only for CSU, and it can also be used in urticaria subjects suffering from recurrent angioedema. The UCT is a 4-item questionnaire for assessing CU disease activity retrospectively over the previous 4 weeks. Each item is rated on a Likert-type scale (0 = very often to 4 = not at all) and a total score is calculated (range, 0 to 16; higher scores indicate better disease control; scores  $\geq 12$  are consistent with well-controlled disease. The higher the achieved score, the higher the level of disease control.

UCT complete response is defined as a score of 16. Clinically relevant response is defined as improvement of 3 or more points in the UCT score (minimal clinically important difference [MCID]). The UCT total score will not be calculated when  $>1$  item within the questionnaire is missing.

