3.8.1 Urticaria Control Test

The Urticaria Control Test (UCT) ([Appendix B.2](#)) is a 4-item questionnaire for assessing CU disease activity retrospectively over the previous 4 weeks. Each item is rated on a Likert-scale (0 = very often to 4 = not at all) and a total score (the sum of all item scores) is calculated (range, 0 to 16; higher scores indicate better disease control; scores ≥ 12 are consistent with well-controlled disease). The UCT total score will not be calculated when ≥ 1 item within the questionnaire is missing.

CR, CMR, and DC for UCT are defined in Section 4.

3.8.2 [REDACTED]

[REDACTED] ([Appendix B.3](#)) is a questionnaire for the last 2 weeks. It comprises [REDACTED] each that are scored from [REDACTED] relating to overall functioning (including work, physical well-being, leisure and social activities), sleep, itching/embarrassment, mental status, swelling/eating, and limits in look (limitations in choice of clothing or cosmetics used due to [REDACTED]). Total scores range from 0 to 100, with higher scores indicating worse [REDACTED]. The [REDACTED] total score will not be calculated when >14 items within the questionnaire are missing. The [REDACTED] domain scores as well as the total score are calculated by using the following formula:

$$\frac{\sum_{\text{nonmissing items}} \text{Item Score Reported}}{\sum_{\text{nonmissing items}} \text{Max Possible Item Score}} \times 100$$

3.8.3

[REDACTED] (Appendix B.4) is a questionnaire for the last 2 weeks. The total score is calculated from the [REDACTED] scores. Score will be calculated using the formula described in Section 3.8.2.

3.8.4

[REDACTED] (Appendix B.5) is a questionnaire for the last 7 days. It comprises [REDACTED] items. Total score will be calculated and converted to the scale of 0-100 using the formula described in Section 3.8.2.

3.8.5

[REDACTED] (Appendix B.6) is a questionnaire for the last 4 weeks. It comprises [REDACTED] items and will be grouped into [REDACTED] domains. The domain and total scores will be calculated and converted to the scale of 0-100 using the formula described in Section 3.8.2.

3.8.6

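### SAP Appendix B.2 keys UCT item 4 backwards: if the primary endpoint is scored as printed, a fully controlled patient totals 12 instead of 16 and the change from baseline shrinks

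*SAP*

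**What the plan says.** SAP 11.5 (Appendix B.2) lists the four UCT questions and states that it gives the points for each answer option. Item 4 asks "Overall, how well have you had your urticaria under control in the last 4 weeks". The options printed beneath it are "very much much somewhat a little not at all", carrying 0, 1, 2, 3 and 4 points in that order. All four items have the same labels and points.

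The same appendix adds the item scores, "with 16 points indicating complete disease control". SAP 3.8.1 agrees: "a total score (the sum of all item scores) is calculated", and "higher scores indicate better disease control". Neither place reverses an item before summing.

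The body text gives one generic anchor for all items. SAP 3.8.1 has "Each item is rated on a Likert-scale (0 = very often to 4 = not at all", and Protocol 10.4.2 has "Each item is rated on a Likert-type scale (0 = very often to 4 = not at all". That anchor suits only item 3, which asks "How often was the treatment for your urticaria in the last 4 weeks not enough to control your urticaria symptoms". Yet Appendix B.2 prints *very much* to *not at all* under item 3 as well, which does not answer a question about frequency.

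**The concern.** Items 1 to 3 ask about suffering, impaired quality of life and insufficient treatment. For these, 0 for *very much* and 4 for *not at all* runs from worst to best. Item 4 asks the opposite kind of question, so under the same key the best answer scores 0 and the worst scores 4. The generic anchor in the body text does not correct this: applied to item 4, *not at all* still earns 4.

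The UCT total drives the primary endpoint (SAP 5.1 and 7.7.1) and the three responder definitions in SAP section 4: CR, CMR and DC. The study has a single treatment and no hypothesis test (SAP 3.3 and 3.5), so the mean change and its confidence interval are themselves the result. No between-arm comparison exists in which a scoring error could cancel.

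The double programming in SAP section 9 shows that two programs agree. It does not show that a key used by both programmers is right.

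**Working it through.** **Inputs.** Four items scored 0 to 4, a plain sum, and 16 meaning complete control (SAP 3.8.1, Appendix B.2). CMR is a rise of at least 3, DC is a total of at least 12, and CR requires both (SAP section 4). Let *a*, *b*, *c*, *d* be the true levels on items 1 to 4, each from 0 (worst) to 4 (best).

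**Formulas.**
- Total in the stated direction: T = a + b + c + d
- Total under the printed key: R = a + b + c + (4 − d) = T + 4 − 2d
- Change under the printed key: ΔR = ΔT − 2Δd
- With s = Δd/ΔT, item 4's share of the change: ΔR = ΔT × (1 − 2s)

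**The plan's own figure.** The plan says complete control scores 16. With d in the stated direction, T = 4+4+4+4 = 16, which reproduces it. Under the printed key, R = 4+4+4+0 = 12, which does not. The worst state gives T = 0 but R = 0+0+0+4 = 4. The worst-to-best span is 12 − 4 = 8, not 16. The numerical range 0 to 16 survives, but the only pattern that reaches 16 is best on items 1 to 3 together with *not at all* under control, which is self-contradictory.

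**Size of the attenuation.** The documents give no item-level data, so s is an assumption:

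| s | ΔR/ΔT |
|---|---|
| 0 | 1.00 |
| 0.20 | 0.60 |
| 0.25 (equal shares) | 0.50 |
| 0.30 | 0.40 |

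In whole scores, a true gain of 8 reads 8, 6, 4 or 2 when item 4 improves by 0, 1, 2 or 3 levels.

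**Effect on responder status.**
- All items from 1 to 3: T goes 4 → 12 (+8; CMR, DC and CR met). R goes 6 → 10 (+4; CMR met, DC and CR missed).
- All items up by one level: ΔT = +4 (CMR met). ΔR = 4 − 2 = +2 (CMR missed).
- Gain confined to items 1 to 3: Δd = 0, so the change is unaffected.
- Of the 16 answer patterns with T ≥ 12 and all items within one level of each other, only 5 have R ≥ 12.

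**The case against.** The strongest reply is that the points may be right and the labels wrong. The answer row of items 1 and 2 looks copied under items 3 and 4, since item 3's labels do not fit its question either. If the form patients saw has correct labels and the stored codes already run from worst to best, the plain sum is correct. Reversing item 4 in the program would then create the error. This stands as a caution about the order of work. It does not rescue the printed key, which contradicts the stated meaning of the total whichever row was miscopied.

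Second, no effect on a result is shown. The eCRF codes and the program are not in the documents, and at s = 0 the effect is nil. That is correct, and the bias is conditional for that reason.

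Third, other safeguards exist. SAP section 9 provides edit checks and monitoring against source, and SAP 6.1 requires listings of all questionnaire data. A 4-4-4-0 pattern could be noticed there, and totals could be recomputed from retained item responses. But no specified check targets the item 4 direction.

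Fourth, Protocol section 13 ranks the SAP above the protocol's analyses and does not settle a conflict inside the SAP. That is fair. The point rests on Appendix B.2 being the only item-level key in either document.

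Finally, figures near items 3 and 4 are missing from the text read here, so the page itself should be looked at. The option and point lines under item 4 are nonetheless complete and in order.

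**Conclusion.** The concern holds. The printed scoring rule for the primary variable contradicts the stated meaning of its total. Followed literally, it gives 12 for full control, 4 for none, and a loss of 2 points for each level gained on item 4. If all four items improve equally, the primary change is halved, and DC, CR and CMR can be missed by patients who truly meet them.

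The 12-versus-16 result is exact. The bias in the trial's results assumes that the printed key reaches the derivation, and its size depends on item 4's share of the change, which the documents do not give. The intended direction is not in doubt. No claim is made about eligibility or other UCT cut-offs applied at sites; these would be affected only if sites scored with this key, which the documents do not show.

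**What to change.** 1. Before database lock, compare Appendix B.2 with the questionnaire as shown to patients, and confirm the direction of the item 4 codes in the eCRF and the derivation program. Change the program only if that check shows item 4 enters the sum in the wrong direction.
2. In Appendix B.2, correct item 4 by meaning: not at all under control = 0, rising to best control = 4. Check item 3's answer labels against its frequency question.
3. In SAP 3.8.1 and Protocol 10.4.2, replace the generic anchor with a statement that every item runs from 0 = worst control to 4 = best control.

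The cost is one key line and one label check in the appendix, one sentence in each document, and a one-off check of the item 4 codes.

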11.6 Appendix B.3

[figure not shown]
11.7 Appendix B.4:

[figure not shown]
11.8 Appendix B.5: 

[figure not shown]

[figure not shown]
Reference: [REDACTED], Version 25 Jul 2017.

[figure not shown]
11.9 Appendix B.6: [REDACTED]

11.10 Appendix B.7:

**11.11 Appendix B.8:** A small black rectangular redaction box is located at the bottom of the page, just above the large redaction area, from approximately y=664 to y=687.

11.12 Appendix C: List of Tables, Listings, and Figures

Table No.	Title	Population

Listing No.	Title	Population

Figure No.	Title	Population

11.13 Appendix D: Table and Listing Shells
